6.2 Screening

Data on the recruitment process will record the number of patients:

- Identified from the initial screening (Direct Care Team)
- Receiving a Patient Information Sheet (site Research Team)
- Who express an interest in participating during the follow up phone call (site Research Team)
- Who are seen in the Surgical Consenting Clinic or Pre-Operative Assessment (site Research Team)
- Who are consented (site Research Team)

At each point, the reason for ineligibility, where known, will be recorded on the REDCap screening log.

Ethnicity data collection for all screened patients will be performed by using the SlicerDicer function on EPIC. This data will be collected anonymously at the end of the recruitment period, or upon request prior to that time point, if required.

6.3 Informed consent

The CI will have overall responsibility for the conduct of research during the trial at the site. This includes ensuring that any site Research Team member delegated to take informed consent has received the appropriate training and is included on the delegation log. This includes Assistant Research Practitioners, Research Practitioners, Research Nurses, Research Co-ordinators and clinicians.

Members of the site Research Team approved to take informed consent will arrange to meet with the patient at either routine Surgical Consenting Clinic or Pre-Operative Assessment appointment. During this appointment the trial will be spoken about in depth, giving the patient the opportunity to ask questions they have concerning trial participation. The patient will decide whether or not they wish to take part, and if they agree to participate they will be asked to provide their written consent using the trial Informed Consent Form (ICF). The site Research Team will explain to the patient that participating in the trial is entirely voluntary and that they have the right to withdraw at any time without needing to provide any reason, or they have the option to flexibly change their participation in the trial by selectively reducing or ceasing any or all of the aspects listed in section 6.8. They will reassure the patient this will in no way prejudice their further treatment.

When completing the ICF, the patient will be asked to read each statement and initial in the relevant boxes if agreeable; they will then sign, print name and date the form, as will the person taking consent. The participant will be given a copy of the signed ICF for their records, a copy will be uploaded to the patient's electronic medical notes on EPIC, and the original will be filed in the Investigator Site File (ISF) held in the site office. The consent discussion will be documented in the patient's electronic medical notes on EPIC by the person who took consent, and the patient will be linked to the trial on EPIC. This will generate an automatic notification to the site Research Team once the patient has been given a surgery date. As per current procedure in the hip unit, time between surgical consent (and therefore trial consent) and surgery is likely to be up to 2-3 months with obviously some surgical administrative variance. The Research Team will also be in communication with the participant's Consultant secretary who will be made aware they need to inform the Research Team once they have given the participant a surgery date also. The Research Team will then be able to plan ahead when the participant is to be randomised.

The participant's GP will be informed of their inclusion into the trial. In addition, once the trial has ended, the GP will be sent a letter notifying them of the treatment allocation received by the participant; please refer to section 6.11 detailing what defines the end of the trial.

A patient is required to reconfirm ongoing participation in the trial if there is a delay of greater than 3 months between consent and date of surgery. The site Research Team will first check if the patient is still happy to continue their involvement in the trial, and if so obtain reconfirmation accordingly. Reconfirmation can either be taken verbally via telephone, or in person at a routine hospital appointment. The Research Team will document this in the patient's medical notes. If the patient no longer wishes to take part in the trial, they can either ask to selectively reduce their participation or fully withdraw from the trial.

When a patient consents to the trial, they will be asked whether they would like to be kept informed about developments of the trial. At the end of the trial all participants will receive a letter notifying them of the treatment allocation they received.

6.4 Participant expenses

The face-to-face visit at 6 weeks post-surgery is part of usual NHS practice. The follow-up visits at 6 months (26 weeks) and 12 months (52 weeks) are both planned to be delivered remotely. Therefore, there is no additional payment for trial participation in terms of travel expenses.

6.5 Randomisation

Participants will be randomised in a 1:1:1 ratio to SPAIRE:PSPA:PA by the ExeCTU. To promote balance across participant characteristics thought to be predictive of outcome, minimisation with a random element will be used. Characteristics of sex (male; female), age (<50; \geq 50 years) and BMI (<30; \geq 30 kg/m²) will be used in the minimisation algorithm (i.e. a total of eight combinations of minimisation factors). The operating surgeon will not be included as a minimisation factor (due to anticipated low inter-operator variability (discussed in greater detail in section 5.2), plus concern that the number of combinations of minimisation factors would be too high if surgeon is included as a factor) but a sensitivity analysis will be performed for the primary outcome measure, to investigate any operator effects.

Participants will be randomised via REDCap within 7 days prior to surgery. Randomisations will be performed, so far as is practically feasible, in strict order by date of scheduled surgery; if more than one participant is scheduled for surgery on the same date, the participants will be randomised in order of age (older age randomised first); if there is more than one participant with the same date of birth they will be randomised in alphabetical order of surname. The member of the site Research Team performing the randomisation will be unaware of previous allocations. If any cases are scheduled at short notice, for various clinical or administrative reasons, then randomisation will be performed as close to 7 days prior to their date of surgery as possible, although this may result in randomisations being performed out of order by date of scheduling. The surgeon and theatre team will still be informed within 24 hours of surgery. If a patient has surgery rescheduled after they have been randomised within 7 days prior to surgery (usually to last minute urgent or trauma cases), their randomisation will be retained. The patient's surgery will be rescheduled for as close as possible to their original date and surgeon/clinical team informed of the randomisation group within 24 hours prior to surgery. The Research Coordinator, Senior Trials Administrator and Team Lead at site will be unblinded and they will be notified of randomised allocation directly from REDCap immediately on randomisation being performed, within 7 days prior to surgery. The operating surgeon and allocated members of theatre staff will be notified of the randomised allocation directly from REDCap within 24 hours prior to surgery. This schedule for randomisation is intended to minimise post-randomisation attrition. Please refer to Table 1 in section 6.6 for summary.

In the event that a participant has been randomised and their planned surgery does not go ahead or they change their mind about participating in the trial, the site Research Team will notify the Trial Manager immediately.

6.6 Blinding

The trial will be double-blinded; the participants will be unaware of which type of surgical approach they have received, and identified members of the site Research Team, which will include the Research Nurse and Research Practitioners who collect outcome data, will also be blinded to the allocated group. Surgeons will remain blinded until the randomisation email is received within **24 hours of surgery**. Operating surgeons will not be involved in collecting any post-operative data. A Senior Statistician will be unblinded throughout the trial to facilitate provision of unblinded reports to the DMC. Blinding of the analysing statistician will be considered, using the Blinding of Trial Statisticians (BOTS) guidance [32]. Use of the BOTS tool will allow a more thorough understanding

of the risks of unblinding of the analysing statistician. However, the default position for the trial will be that the trial statistician (performing data analysis) will remain blinded until the presentation of the primary analyses of the primary and secondary outcome data. At this point, the wider trial team will be unblinded. The remaining analyses will then be performed with the statistician unblinded. Any deviation from this position will be made in the light of the risk assessment derived from the BOTS tool. The Research Coordinator, Senior Trial Administrator and, by means of contingency, the Research Team Lead, will be unblinded and will randomise participants via REDCap within **7 days prior to surgery**; they will also enter the surgical data to the trial database. Post-operative care does not differ between each technique, and the surgical dressing is applied to the same site over the hip area and cannot be distinguished between each approach. The documentation about the surgical approach in the operation notes will not specify which technique was used for the procedure and will state that the patient is enrolled in the HIPSTER research trial. Table 1 below summarises the planned blinding status for key personnel.

BLINDED	Notified of treatment allocation when?	How?
	At end of trial (as defined in	Via letter from site
Participants	section 6.11), if requested.	Research Team
Site Research Team* (co- ordinating follow-ups)		
	Up to 24 hours prior to	
Surgeon	surgery	Automatically via REDCap
Trial Statistician	To be unblinded to participant allocations following presentation of primary analyses	Unblinding to take place during meeting where results are presented, by unblinded member of trial team who is aware of group allocations
UNBLINDED		
Research Coordinator (RDE)/Trial Manager (no post-op data collection or involvement)	Up to 7 days prior to surgery	Automatically via REDCap
Site Senior Research Administrator (RDE)	Up to 7 days prior to surgery	Automatically via REDCap
Site Research Team Lead (RDE)	Up to 7 days prior to surgery	Automatically via REDCap
Senior Statistician		

Table 1: Blinding status to individual participant treatment allocations

*Research Nurse, Research Practitioners

The week prior to surgery, the hip Multidisciplinary Team will meet to discuss the following week's surgical cases. In this meeting, patients will be identified as participants in the HIPSTER trial; however, no information regarding the trial treatment arm will be discussed. The operating surgeon will receive the treatment allocation via an email from REDCap within 24 hours of surgery. The theatre team will be made aware of a participant's randomised allocation within 24 hours of surgery by the operating surgeon. The theatre kits for the SPAIRE, PSPA and PA approach will always be available in theatre and therefore the theatre team will not need to be notified more than 24 hours prior to surgery and can remain blinded until that point.

6.6.1 Emergency unblinding

We do not expect a situation to arise where knowledge of exact surgical technique used will be needed to inform any urgent medical management. As such, no special emergency unblinding process is required, but surgical details can be obtained within normal working hours from the site Research Team.

6.7 Trial assessments

6.7.1 Schedule of events

	Time point								
	Pre-op			Post-op					
Assessment/visit	Screening	Pre-op assessment (baseline)	7 days prior to surgery (Research Team)	24 hours prior to surgery (Surgeon & theatre staff)	Day 0/1 (inpatient)	Notes review after discharge	6 weeks (+/- 2 weeks)	6 months (26 weeks) (-4 weeks/+12 weeks)	12 months (52 weeks) (-4 weeks/+12 weeks)
Check eligibility and provide PIS	Х								
Confirm inclusion/exclusion criteria		Х							
Consent		Х							
Demographic data (name, DOB, sex of patient, height, weight, BMI, ethnicity), any existing comorbidities, and contact details		X							
Blood biomarkers – CK and CRP		Х			Х		Х		
Activity monitor issued in clinic and prepaid returns envelope provided		X					X		
PROMs – OHS, LEFS, EQ-5D-5L in clinic		Х							
Randomisation			Х	Х					
Check pre-operative imaging has been requested by surgeon (imaging to be done within 3 months of surgery date)		X							
Peri-operative data: length of stay ¹ , surgery time, blood loss, conversion of allocated randomisation approach ²						X			
PROMs – OARS, OACS, OHS, LEFS, EQ-5D-5L, SAPS in clinic							X		
Activity monitor issued via post and prepaid returns envelope provided								Х	Х
PROMs – OHS, LEFS, EQ-5D-5L, SAPS remotely								Х	Х
Additional analgesia use							Х		
Safety reporting – AEs and SAEs					Х	Х	Х	X	Х
Additional surgical procedures								X	Х
¹ Length of stay is recorded at time of discharge, i.e. converted to another during surgery (SPAIRE to PS	number of n PA or PA; or	ights a participa PSPA to PA).	int stays in	hospital post-	surgery. ² Co	nversion of a	pproach recor	ds if the intende	ed approach is

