The Data Monitoring Committee (DMC) will be composed of a minimum of three independent professional members, including a statistician. The CI and Co-CI, Senior Trial Statistician and Trial Manager will be invited to attend the open sessions of DMC meetings but will not be voting members. The Senior Trial Statistician will be unblinded throughout the trial and the Trial Statistician will remain blinded until completion of the primary analyses for the primary and secondary outcomes. Only the unblinded statistician(s) can be invited to the closed section of DMC meetings and will prepare/review unblinded sections of the DMC report. The DMC will monitor accumulating trial data, including safety, and make recommendations to the TSC as to whether there are any ethical or safety issues that may necessitate a modification to the protocol or early closure of the trial. The DMC will meet prior to recruitment commencing and at least 6-monthly thereafter. Further details of the roles and responsibilities of the DMC are documented in the DMC charter, available upon request to the Trial Manager.

Patient Advisory Group

An overarching Patient Advisory Group led by the PPIE lead will review patient-facing materials prior to ethical review and will have input into any revisions to patient-facing materials throughout the trial. This group will meet once a year.

The Site Research Team

The site Research Team will be responsible for the delivery of trial activities on site. This team consists of Research Nurses, Research Practitioners and a Senior Trials Administrator. The site Research Team is led by the Team Lead and will work closely with the Trial Manager/Research Co-ordinator and clinicians.

KEYWORDS

Total hip replacement; total hip arthroplasty; posterior approach; piriformis sparing posterior approach; spare piriformis and internus repair externus; double-blind, parallel three-arm, randomised-controlled, superiority trial

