Participants who have opted for paper PROMs will have these posted to them by the site Research Team, with a prepaid return envelope provided.

Physical activity monitor and instructions to be issued via post for participant to wear for 2 consecutive weeks, and a prepaid return envelope provided.

Report any AE/SAEs, and document any additional surgical procedures that have occurred within 26 to 52 weeks post-operative; this is done via telephone call or email to participant. Participant will be reminded to return activity monitor. Medical notes also to be reviewed for any SAEs.

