7.3 Reporting adverse events

All reportable AEs/SAEs/RUSAEs should be recorded from the point of surgery to the end of trial participation at 12 months (52 weeks) follow-up post-operatively.

SAEs must be reported directly onto REDCap **within 24 hours** of the blinded site Research Team becoming aware of the event. SAEs classed as possibly, probably or definitely related AND unexpected (RUSAEs) will be reported by ExeCTU to the Sponsor within 24 hours of ExeCTU staff becoming aware. The Sponsor is responsible for onward reporting of RUSAEs to the REC within 15 days of the event being reported to ExeCTU in REDCap. However, if the event results in death the SAE will be reported to the REC within 7 days of the event being reported to ExeCTU in REDCap.

The CI (in their role as site PI) or their delegate, is responsible for signing off reportable SAEs within the EDC system. This will be a role restricted task that only authorised users of the EDC can complete.

For each SAE the following information will be collected:

- full details in medical terms and case description
- event duration (start and end dates, if applicable)
- action taken
- outcome
- seriousness criteria
- causality (i.e. relatedness to intervention)

Any change of condition or other follow-up information should be updated directly onto REDCap as soon as it is available. Events will be followed up until the event has resolved or a final outcome has been reached. An outcome of 'unknown' is not considered to be an acceptable final outcome. An outcome of 'not yet resolved' is an acceptable final outcome for non-serious AEs at the end of a participant's involvement in a trial, and for SAEs at database lock.

Where SAE causality is initially assessed by an authorised delegate of the CI but not the CI themselves, the CI (in their role as CI, as opposed to site PI) will record a second assessment of causal relationship. The CI may upgrade the causality assessment (e.g. from not related to related) but may not downgrade the assessment (e.g. related to not related). Where a causal relationship is suggested, the CI will record an assessment of expectedness.

The TSC and DMC will periodically review SAE data to determine patterns and trends of events, or to identify safety issues, which would not be apparent on an individual case basis.

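### The SAE reporting clocks start from three different triggers, one of which omits unblinded staff, and a last contact at week 48 can leave up to 4 of the 52 safety weeks unsearched

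*Protocol*

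**What the plan says.** **Reporting clock.** Section 7.3 asks for SAEs to be entered in REDCap within 24 hours "of the blinded site Research Team becoming aware of the event". Section 7.2.4 sets a 24-hour limit for assigning causality, counted from awareness by the site. Section 7.4 gives 24 hours for a death, counted from its identification, with no condition on who identifies it. Section 6.6 and Table 1 make the Research Coordinator, the Senior Trials Administrator and the Team Lead unblinded, and have unblinded staff enter the surgical data. The operating surgeon learns the allocation in the last 24 hours before surgery. Section 6.7.4 requires events during surgery to be reported.

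**Contacts.** The schedule in section 6.7.1 sets the follow-up points at "6 weeks (+/- 2 weeks", "6 months (26 weeks) (-4 weeks/+12 weeks" and "12 months (52 weeks) (-4 weeks/+12 weeks" (closing brackets omitted). Its safety row is also marked at Day 0/1 and at "Notes review after discharge". Section 6.7.5 adds an EPIC review for the inpatient stay. The 26- and 52-week contacts are remote, and for both the protocol adds: "Medical notes also to be reviewed for any SAEs".

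**Safety period.** Sections 3.2 and 3.5 run safety from the day of surgery to 52 weeks. Section 7.3 ends recording at the 12-month follow-up, and section 6.11 ends the participant's involvement there. The stated recall intervals are surgery to 6 weeks (6.7.6), 6 to 26 weeks (6.7.7) and 26 to 52 weeks (6.7.8).

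**Oversight.** "The DMC will meet prior to recruitment commencing and at least 6-monthly thereafter". Section 7.3 has the DMC and TSC review SAE data periodically.

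**The concern.** Two things do not fit together. First, a clock tied to the blinded team excludes, on its wording, the people most likely to witness a serious event in theatre. The causality clock in 7.2.4 could even run out before the entry clock in 7.3 has started, because awareness by the site can come before awareness by its blinded members.

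Second, the safety objective is fixed at 52 weeks, but the contact that closes it may come earlier, and the recall intervals are tied to nominal weeks rather than to the dates on which participants are actually contacted.

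At stake are prompt entry of intra-operative SAEs and a safety count with the same observation period for every participant. Section 8.9 reports SAEs descriptively by treatment received, so there is no model with time at risk to absorb unequal observation.

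**Working it through.** The protocol gives windows but no gap or detection delay, so there is no stated figure to reproduce. The check sets the texts side by side and does the window arithmetic.

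**1. The three triggers**

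| Section | What must happen in 24 hours | Clock starts at |
|---|---|---|
| 7.3 | SAE entered in REDCap | awareness by the blinded site team |
| 7.2.4 | causality assigned, otherwise expedited reporting | awareness by the site |
| 7.4 | death reported as an SAE | identification of the death |

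A death is an SAE, so 7.3 and 7.4 both apply to it with different starts. For an intra-operative SAE, the surgeon and the unblinded staff belong to the site (7.2.4) but not to the blinded team (7.3). Section 7.3 does not require them to tell blinded staff.

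**2. Contact windows (from 6.7.1)**

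- 6-week visit: 6 − 2 = week 4 to 6 + 2 = week 8
- 26-week contact: 26 − 4 = week 22 to 26 + 12 = week 38
- 52-week contact: 52 − 4 = week 48 to 52 + 12 = week 64

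**3. End of the safety period**

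The earliest last contact is week 48. Involvement ends there (6.11), and no later search is stated. Unsearched time is 52 − 48 = 4 weeks, and 4/52 = 7.7% of the defined period. This is the maximum for one participant; someone contacted at week 52 or later loses nothing.

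**4. Recall intervals**

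A contact at week 22 can cover only up to week 22, and the next stated interval opens at week 26. So 26 − 22 = 4 weeks lie outside both intervals as worded. In 6.7.7 and 6.7.8 the interval may grammatically attach only to additional surgical procedures, and the notes review has no stated interval, so a full review might still find such events.

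**5. Gaps between scheduled searches after the 6-week visit**

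Longest gap = latest later contact − earliest earlier contact; shortest gap = earliest later contact − latest earlier contact.

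| Interval | Planned | Shortest | Longest |
|---|---|---|---|
| 6 to 26 weeks | 26 − 6 = 20 | 22 − 8 = 14 | 38 − 4 = 34 |
| 26 to 52 weeks | 52 − 26 = 26 | 48 − 38 = 10 | 64 − 22 = 42 |

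Section 7.2.3 lists expected operation-related events within 12 weeks of surgery. An event at week 12 that came to light only at the next contact would be found 22 − 12 = 10 to 38 − 12 = 26 weeks later.

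**The case against.** The strongest reply is that safety capture is wider than the contact dates suggest. There is an inpatient EPIC review and a notes review after discharge, and the two remote contacts add notes reviews. The 24-hour rule applies whenever the team becomes aware, at a contact or not. Sections 6.7.4 and 6.7.5 should bring intra-operative events to the research team. The spacing of contacts is a design choice, and a DMC charter and a monitoring plan, neither shown here, may contain further checks. The possible loss at the end is at most 4 weeks, well after the 12-week period for operation-related events, and no reason is apparent why it should differ between arms. All of this stands, and it limits the point. It does not reconcile the three triggers or supply a search of weeks 48 to 52.

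Four stronger inferences are tempting, and the protocol does not support them:

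- **That SAEs are sought only at visits.** The record reviews above contradict this. What is absent is a scheduled search between contacts.
- **That gaps of 34 to 42 weeks are typical.** These are the extremes of two different intervals, each needing one contact at its earliest limit and the next at its latest. The planned gaps are 20 and 26 weeks.
- **That a contact at week 64 adds 12 weeks to the safety count.** Sections 3.2, 3.5 and 6.7.8 all stop at 52 weeks, so later events need not be counted.
- **That the DMC sees harms late and incompletely, with a calculable number of patients randomised meanwhile.** One participant's longest gap is not a trial-wide delay, because other participants' events keep arriving. The protocol gives no SAE rates or actual contact dates.

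**Conclusion.** The point holds as a defect of wording and coverage that should be corrected; it does not show that SAEs have been lost. The triggers in 7.2.4, 7.3 and 7.4 conflict, and read literally 7.3 ignores the knowledge of surgeons and unblinded staff. The schedule lets the last safety contact precede the end of the defined period by up to 4 weeks (7.7%), and an early 26-week contact opens a similar 4-week hole between the recall intervals.

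These sizes are maxima per participant. They assume contacts at the early limits of the windows and no notes review after the contact. How many participants are affected cannot be derived from the protocol. Late DMC awareness is possible, since even the planned 26-week gap is about as long as the interval between DMC meetings, but it cannot be quantified. The safety flowchart in 7.3.1 is a figure not shown in the text examined; its trigger should be checked when the wording is aligned.

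**What to change.** 1. **One trigger.** Reconcile 7.2.4, 7.3, 7.4 and the flowchart so that each 24-hour clock starts when any delegated trial staff member becomes aware, including the operating surgeon and unblinded staff. Make the entry without naming the surgical approach, so that blinding is kept.
2. **One safety period.** Do the final SAE notes review no earlier than week 52, and count events to day 364 (52 × 7) for everyone. Word the recall question at each contact to run from the previous actual contact rather than from a nominal week.
3. **Optional.** Run an EPIC notes check for SAEs on all participants at each DMC data cut.

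None of this depends on new automatic alerts. The only EPIC notice that section 6.3 describes concerns surgery dates ("This will generate an automatic notification to the site Research Team once the patient has been given a surgery date"), and the protocol does not show that it could be extended to admissions.

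The cost is wording changes in sections 6.7 and 7, one later notes check for participants contacted before week 52, and modest extra staff time if the optional check is adopted.
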